## 4.5.2 Randomization/Participant Registration

At entry, participants will be enrolled according to standard ACTG DMC procedures.

For participants from whom informed consent has been obtained, but who are deemed ineligible or who do not enroll into the initial protocol step, an ACTG Screening Failure Results form must be completed and keyed into the database.

#### 4.6 Coenrollment Guidelines

US sites are encouraged to coenroll participants in A5128, "Plan for Obtaining Informed Consent to Use Stored Human Biological Materials (HBM) for Currently Unspecified Analyses."

If there are concerns about exceeding volume limits for blood draws, please note that A5128 allows participants to consent to the study without allowing a blood sample to be collected. In these cases, if a future study wants to evaluate a participant's DNA sometime later, sites would be able to access a stored aliquot from the initial study (if there are any available). It is also possible for a participant to enroll into A5128 and postpone the required blood draw until a later time. For more input, contact the A5128 team.

## 5.0 STUDY TREATMENT

A5348 study treatment drugs are defined as ledipasvir (90mg)/sofosbuvir (400mg) (LDV/SOF) (brand name: Harvoni) and weight-based ribavirin (RBV).

5.1 Regimens Administration, and Duration

In this phase II retreatment study, a total of 40 participants will be randomized at entry in 1:1 open-label fashion to Arm A or Arm B (20 participants per arm), as outlined in Tables 5-1 and 5-2.

## Table 5-1: A5348 Treatment Regimen

Weeks	Arm A	Arm B (no RBV)
1-12	LDV 90 mg/SOF 400 mg fixed dose tablet once daily PLUS Ribavirin, based on weight at entry For weight <75 kg: 1000 mg per day* For weight > 75 kg: 1200mg per day*	LDV 90 mg/SOF 400 mg fixed dose tablet once daily
13-24	No treatment	LDV 90 mg/SOF 400 mg fixed dose tablet once daily

\*Total daily dose of ribavirin has been divided into two doses. The dose of ribavirin will be based on participant's weight at entry. Changes in weight after entry do not require a change in dose. Doses will only be changed for toxicity management. Ribavirin will be available as ribavirin 200mg tablets.

Table 5-2: Weight-based	Ribavirin Dose
-------------------------	----------------

Weight (kg)	Morning Dose	Evening Dose
< 75 kg	600 mg	400 mg
> 75 kg	600 mg	600 mg

#### 5.1.1 Administration

Ledipasvir/sofosbuvir should be taken with morning or evening ribavirin, if assigned to a ribavirin-containing therapy (Arm A). Participants should be instructed to take all doses of study drug with food. Study drug should be taken at the same times and maintain the same time intervals every day.

If a participant forgets to take the ledipasvir/sofosbuvir at the correct time, it may be taken later in the day; however, no more than one tablet of ledipasvir/sofosbuvir should be taken on any calendar day. The participant should resume the standing dosing schedule on the next day. Study medications should not be cut or split. If participants miss a dose of ribavirin, they should take the missed dose as soon as possible with food during the same day. If an entire day has gone by, then the missed dose should be skipped, and the normal dosing schedule should be resumed. Participants should not double the next dose of either study drug in order to "make up" what had been missed.

# 5.1.2 Duration

Study treatment may continue for a period of 12 or 24 weeks (as assigned at study entry). Study follow-up will be for 24 weeks after treatment completion.

# 5.2 Study Product Formulation and Preparation

# 5.2.1 Formulation

Ledipasvir (90 mg) /sofosbuvir (400 mg) (brand name: Harvoni) is a fixed-dose combination tablet. It is an orange colored, diamond shaped, film-coated tablet debossed with "GSI" on one side and "7985" on the other side of the tablet. Each tablet contains ledipasvir (90 mg) /sofosbuvir (400 mg) as active ingredient. In addition to the active ingredients, ledipasvir (90 mg) /sofosbuvir (400 mg) tablet contain the following inactive ingredients: colloidal silicon dioxide, copovidone, croscarmellose sodium, lactose monohydrate, magnesium stearate, and microcrystalline cellulose.

Ribavirin will be supplied as tablets for oral administration, each containing 200 mg of ribavirin.

# 5.2.2 Storage

Bottle containing ledipasvir (90 mg) /sofosbuvir (400 mg) should be stored at a controlled room temperature. Controlled room temperature is defined as 25°C (77°F); excursions are permitted between 15°C and 30°C (59°F to 86°F).

Ribavirin tablets should be stored at 20°C - 25°C (68°F - 77°F).

# 5.3 Pharmacy: Product Supply, Distribution, and Accountability

# 5.3.1 Study Product Acquisition/Distribution

Gilead Sciences, Inc. will provide ledipasvir (90 mg) /sofosbuvir (400 mg) for this study; ribavirin will be provided through the study. Study products will be available through the NIAID Clinical Research Products Management Center (CRPMC). The site pharmacist should obtain the study products for this protocol by following the instructions in the manual *Pharmacy Guidelines and Instructions for DAIDS Clinical Trials Networks* in the section *Study Product Management Responsibilities*.

ARV will not be provided through the study.

5.3.2 Study Product Accountability

The site pharmacist is required to maintain complete records of all study products received from the NIAID CRPMC and subsequently dispensed. All unused study products in US CRSs must be returned to the NIAID CRPMC (or as otherwise directed by the sponsor) after the study is completed or terminated. The procedures to be followed are in the manual *Pharmacy Guidelines and Instructions for DAIDS Clinical Trials Networks.* 

## 5.4 Concomitant Medications

Whenever a concomitant medication or study agent is initiated or a dose changed, investigators must review the concomitant medication's and study agent's most recent package insert, Investigator's Brochure, or updated information from DAIDS to obtain the most current information on drug interactions, contraindications, and precautions. Additional drug information may be found on the updated ACTG Drug Interactions Database located at: http://tprc.pharm.buffalo.edu/home/di\_search.

## 5.4.1 Required Medications

See inclusion criteria (section 4.1.5) for specifications about ARV. Changes to ARV must be discussed with the A5348 protocol core team during the study drug dosing period.

#### 5.4.2 Prohibited Medications

For a list of prohibited medications, please refer to the A5348 PSWP, as well as the ledipasvir/sofosbuvir package insert, which is available on the A5348 PSWP.

#### 5.4.3 Precautionary Medications

For a full list of precautionary medications, please refer to the ledipasvir/sofosbuvir package insert, which is available on the A5348 PSWP.

H2-receptor antagonists may be administered simultaneously with or 12 hours apart from ledipasvir/sofosbuvir at a dose that does not exceed doses comparable to famotidine 40 mg twice daily.

Proton-pump inhibitor doses comparable to omeprazole 20 mg or lower should only be administered simultaneously with ledipasvir/sofosbuvir under fasted conditions.

#### 5.4.4 Colony Stimulating Agents

Under no circumstances are potential participants to be treated with colony stimulating agents during screening to elevate hematology laboratory parameters to facilitate entry into the study. Colony stimulating agents, such as

erythropoiesis stimulating agents or granulocyte colony-stimulating factor, will not be provided by the study.

# 6.0 CLINICAL AND LABORATORY EVALUATIONS

# 6.1 Schedule of Events

						ST	EP 1					STEP 2		c	Ľ	
Evaluations	Screening (Within 42 days prior	Entry	C	)n-Treat	ment (A Week		-	On-Ti	On-Treatment (Arm B only) Week			Post-Treatment (Arms A&B) (R=Date of Last Dose of Study Treatment) Week			HIV-1 VF Confirmation	Prem. Tx/Study Discontinuation 
	to entry)		1	2	4	8	12 	16	20	24 	R+4	R+12	R+24	HCV VF Confirmation	1 VF (	o rem. Viscon
			•	nin ± 3 ays)		(	(Within :	±7 days	5)	•	(Within -5 to +7days)	(Within -5 to +14days)	(Within -7 to +14days)	HC	->IH	
HIV-1 Documentation	х															
Cirrhosis Status Documentation	х															
Documentation of HCV Treatment	x	х														
Medical History	х	х														
Medication History	х	х														
Clinical Assessments	х	х	Х	Х	Х	Х	Х	х	Х	Х	х	Х	Х			х
Height	Х															
Weight	Х	Х	Х	Х	Х	Х	Х	Х	Х	Х	Х	Х	Х			Х
BMI	Х															
12-Lead ECG	Х															
Hematology & Chemistries	Х	Х	х	Х	Х	Х	Х	Х	Х	Х	х	Х	Х			х

						STI	EP 1				STEP 2			с	Ľ	
Evaluations	Screening (Within 42		С	)n-Treat	ment ( F Week	Arms A&	в)	On-Ti	On-Treatment (Arm B only) Week			Post-Treatment (Arms A&B) (R=Date of Last Dose of Study Treatment) Week			HIV-1 VF Confirmation	Prem. Tx/Study Discontinuation 
	days prior to entry)		1	2	4	8	12 	16	20	24 	R+4	R+12	R+24	HCV VF Confirmation	1 VF	rem. iscon
Liver Function			``	nin ± 3 ays)			(Within :	± 7 days	5)		(Within -5 to +7days)	(Within -5 to +14days)	(Within -7 to +14days)	HCV	->IH	L C
Liver Function Tests	x	х	Х	х	Х	х	х	Х	Х	x	Х	Х	x			х
Hgb A1c	X															
Uric Acid		Х					Х			Х						
Calculated CrCl	x	х	Х	х	Х	х	Х	Х	Х	x	Х	Х	Х			х
Lipid Panel (fasting) 		х					х			x						х
INR	Х	Х					Х			Х						Х
Urinalysis		Х	X 	X 	Х	X 	Х	X 	Х	X 	X 					
Urine for spot protein and creatinine		х			_			As inc	dicated	(see sec	ction 6.3.7)					
Serum Pregnancy Test 	х	х														
Urine Pregnancy Test			х	Х	х	x	x	х	х	х	Х	х	х			x
HBsAg	x															
HCV RNA Local lab	х															

	Screening (Within 42					ST	EP 1				STEP 2			c	u		
Evaluations		Entry	0	n-Treat	ment (A Week	Arms A&	в)	On-Tr	On-Treatment (Arm B only) Week			Post-Treatment (Arms A&B) (R=Date of Last Dose of Study Treatment) Week			Confirmation	Prem. Tx/Study Discontinuation 	
	days prior to entry)			1	2	4 8 12 		12 	16	20	24 	R+4	R+12	R+24	HCV VF Confirmation	HIV-1 VF (	rem.
HCV RNA			``	in ± 3 ys)		(	(Within :	± 7 days	5)		(Within -5 to +7days)	(Within -5 to +14days)	(Within -7 to +14days)	НС	-VIH	άä	
HCV RNA (Real time)		х	х	х	х	х	х	x	x	x	х	x	х	х		х	
Plasma HCV Genotype Test	х													х			
HCV Resistance Testing		х												х			
Stored Plasma for HCV Studies (see section 6.3.8)		x	х	x	x		x			x				х		x	
Plasma HIV-1 RNA (real- time)⁵	х	X 			X 		X 			X 	X 				X 	X 	
Plasma HIV-1 RNA Resistance Testing															х		
CD4+/CD8+	Х	Х					Х			Х						Х	
Stored Whole Blood Sample for Future Genetic Testing		х															
Stored Urine		Х			Х		Х			Х	Х					Х	

						STE	EP 1					STEP 2		L	Ľ							
Evaluations (Within days pl	Screening (Within 42	Entry	On-Treatment (Arms A&B) Week						On-Treatment (Arm B only) Week			Post-Treatment (Arms A&B) (R=Date of Last Dose of Study Treatment) Week			Confirmation	Prem. Tx/Study Discontinuation 						
	to entry)			-	-				1	2	4	8	12 	16	20	24 	R+4	R+12	R+24	HCV VF Confirmation	HIV-1 VF	rem. iscon
			``	in ± 3 ys)		(	Within ±	E 7 days	5)	I	(Within -5 to +7days)	(Within -5 to +14days)	(Within -7 to +14days)	HCV	-VIH	ша						
TFV PK Evaluation (pre-dose, 1hr, 4hr)  (FASTING)		x			x																	
Dried Blood Spots for PK		х	х	х	х	х	х	х	х	х	Х											
IL-28B Genotype		х																				
Pregnancy Prevention Counseling	х	х			х		х				х					х						
Adherence Assessments (4 day recall, pill counts)			х	х	х	х	х	х	x	х												
Study Drug Dispensing		х			х	х	х	х	х													
Medication Diary  (D=distribution, C=collect)		X (D)	X (C/D)	X (C/D)	X (C/D)	X (C/D)	X (C/D)	X (C/D)	X (C/D)	X (C/D)	X (C)											

#### NOTES

Refer to Section 6.2.3 regarding registration into Step 2.

 Participants must be fasting for visits at entry, weeks 12, and 24, and premature discontinuation. If not fasting, they should return within 7 days of the visit to repeat the lipid panel that require fasting per section 6.3.7 and within 48 hours fasting to complete the tenofovir PK evaluation, if applicable.

 Urinalysis at this timepoint is required only for participants on tenofovir/ritonavir-boosted HIV protease inhibitor.

Females must have a negative serum pregnancy test with a sensitivity of at least 25 mIU/mL performed at screening and within 48 hours prior to study entry.

HIV RNA after screening is only required if participant is taking ARV.

 For participants on tenofovir and PI/r only. Participants should be in a fasting state until after the 1 hour post dose PK blood draw is obtained.

 Use of medication diary is recommended for the two PK visits and is optional for dried blood spot visit (see section 6.3.17).

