# NOTE: ECG abnormalities that are not of clinical concern for underlying heart conditions that may be exacerbated by ribavirin are not exclusionary.

12. Section 6.1, Schedule of Events, footnotes #3 and 6 has been revised to strike "tenofovir" and replace with **TDF**.

13. Section 6.3.6, Clinical Assessments, Complete Physical has been revised, removing standardized blood pressure. The revised language reads as follows:

A complete physical examination must be performed at screening and is to include at a minimum an examination of the head, neck and thyroid; eyes, ears, nose, throat, mouth and tongue; chest (excluding breasts); respiratory; cardiovascular; lymph nodes, abdomen; skin, hair, nails; musculoskeletal; neurological.

The complete physical exam will also include diagnoses, signs, and symptoms and vital signs (temperature, pulse, respiratory rate, and resting blood pressure).

NOTE: Blood pressure will be measured following the current ACTG Standardization of Blood Pressure Measurement SOP.

- 14. Section 6.3.7, Laboratory Evaluations, Urinalysis has been revised to strike "tenofovir" and replace with **TDF**.
- 15. Section 6.3.11, Tenofovir PK Samples, first sentence has been revised and now reads:

The tenofovir PK sampling evaluations will be only required for the first 15 participants, and consenting participants thereafter, who are taking ritonavir-boosted protease inhibitor and **TDF-containing ART** tenofovir.

- 16. Section 7.1.3.1, Specific Guidance for Creatinine Clearance, fifth bullet has been revised to strike "tenofovir" and replace with **TDF**.
- 17. Section 9.3, Randomization and Stratification has been revised and now reads:

The study is randomized to Arm A and Arm B and stratified by the cirrhosis status. Initially, 15 slots will be reserved for participants taking a PI/r and tenofovir **TDFcontaining** regimen across the two study arms. This will be lifted 3 months after the study is open to accrual, so that the accrual progress is not constrained by the PK objective on tenofovir.

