#### Step 2: Post-Treatment Evaluations

Participants will be registered to Step 2 at their last on-treatment visit. R is the date of the last dose of study treatment. Arm A participants will register to Step 2 at week 12. Arm B participants will register to Step 2 at week 24. Participants who prematurely discontinue study treatment will register to Step 2 at the premature treatment discontinuation visit.

After the last dose of study drugs, the post-treatment study visits have the following windows:

- Week R+4: -5 days to +7 days
- Week R+12: -5 days and +14 days
- Week R+24: -7 days and +14 days

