## Premature Treatment Discontinuation Evaluations

The protocol core team must be informed, as soon as possible, when a participant prematurely discontinues study treatment due to an AE. Participants who permanently discontinue study treatment for toxicity or any other reason, and who have not met the HCV virologic failure criteria defined in section 7.3 will also follow the Step 2 schedule in section 6.1. If applicable, additional or more frequent post-treatment toxicity follow up may be determined by the site

investigator.

Participants who prematurely discontinue study treatment (i.e., prior to completion of the last dose of LDV/SOF per the assigned dosing period) will complete the premature treatment discontinuation evaluations within 7 days of discontinuation and be registered to Step 2 (R). Participants will remain on study and complete the post-treatment visits at weeks R+4, R+12, and R+24 weeks per the SOE.

Participants who prematurely discontinue the study treatment for any reason will register for Step 2 at their Premature Treatment Discontinuation Visit.

NOTE: If LDV/SOF is discontinued, Arm A participants should discontinue RBV. Under no condition should the participant remain on RBV monotherapy.

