#### Blood Chemistries

Sodium, potassium, chloride, bicarbonate/CO2, blood urea nitrogen (BUN), creatinine, glucose, and lipase.

Uric Acid: required at weeks 0, 12, and 24.

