## Stored Urine

Urine will be collected and stored for evaluation of retinol binding protein, beta-2 microglobulin, and creatinine. Refer to A5348 LPC for instructions.

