The study regimens have different treatment durations and, while the post-treatment follow-up time is the same for both study arms, the study durations are different in Arms A and B. Assessment of reasons for not achieving SVR12 is an important part of SVR12 and SVR24 analyses in this study, including loss to follow-up. Differential loss to follow-up in the two study arms may suggest the benefit of the shorter duration in the 12-week regimen or drawback of RBV intolerance. Either way, the SVR endpoints would capture the outcome of the regimen.

- 9.2 Outcome Measures
  - 9.2.1 Primary Outcome Measures
    - 9.2.1.1 SVR12 defined as HCV RNA < lower limit of quantification (LLOQ) (either target detected [TD] or target not detected [TND]) at 12 weeks after treatment discontinuation. The sample within the week R+12 (post-treatment) visit window, as defined in section 6.0, which is closest to the targeted time will be used. If there is no HCV RNA sample within this window, then the participant will be considered SVR12 failure, unless there are preceding and subsequent HCV RNA measurements that are both <LLOQ (either TD or TND).

    - 9.2.1.2 Occurrence of Grade 3 or higher AE (diagnosis, sign, symptom, or laboratory abnormality), SAE according to ICH criteria, or AE reported as the reason for permanent discontinuation of study treatment, during study treatment and up to 30 days after study treatment discontinuation. (Event that is ongoing at the same grade from prior to study treatment initiation will be excluded.)
  - 9.2.2 Secondary Outcome Measures
    - 9.2.2.1 Renal toxicity: (a) ≥ Grade 2 creatinine clearance after study entry, or
       (b) new proteinuria and/or glucosuria, defined as ≥ 1+ or an increase ≥ 1+ from baseline.
    - 9.2.2.2 SVR4 defined as HCV RNA < LLOQ (either TD or TND) at 4 weeks after treatment discontinuation. The measurement within the week R+4 visit window that is closest to the targeted time will be used. If there is no HCV RNA sample within this window, then the participant will be considered SVR4 failure, unless there are preceding and subsequent HCV RNA measurements that are <LLOQ (either TD or TND).

- 9.2.2.3 SVR24 defined as HCV RNA < LLOQ (either TD or TND) at 24 weeks after treatment discontinuation. Sample after 20 weeks after treatment discontinuation that is closest to the targeted time, not followed by any result ≥LLOQ, will be used.

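### No urinalysis is scheduled at premature discontinuation for anyone, or after week 20 for Arm B participants not on TDF plus PI/r, although the urine part of the renal outcome covers all participants

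*Protocol*

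**What the plan says.** The urinalysis row of the Schedule of Events (Protocol 6.1) has unrestricted marks at entry and weeks 4, 12 and 20. The marks at weeks 1, 2, 8, 16, 24 and R+4 carry footnote 3: "Urinalysis at this timepoint is required only for participants on tenofovir/ritonavir-boosted HIV protease inhibitor". Item 12 of Letter of Amendment #1 ("Section 6.1, Schedule of Events, footnotes #3 and 6 has been revised to strike") replaces tenofovir with TDF, so the restricted group is now TDF plus PI/r. The cells for R+12, R+24, both virologic failure confirmations and premature treatment/study discontinuation are blank.

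Protocol 9.2.2.1 defines renal toxicity as either (a) creatinine clearance of Grade 2 or worse, or (b) "new proteinuria and/or glucosuria, defined as ≥ 1+ or an increase ≥ 1+ from baseline". Neither limb is restricted by ARV regimen. SAP 4.2.1(c) lists participants with these events, also without restriction.

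Arm B ends treatment at week 24: "Arm B participants will register to Step 2 at week 24". Calculated CrCl, chemistries and stored urine are all scheduled at week 24 and at premature discontinuation for everyone.

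**The concern.** The outcome is defined for the whole trial, but the test that detects its second limb is not scheduled for the whole trial at the time treatment ends. Limb (b) is joined to limb (a) by an *or*, so it is meant to pick up proteinuria or glucosuria that occurs without a fall in creatinine clearance. Those are the events with no scheduled test late in Arm B (outside TDF plus PI/r) or at an early stop.

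The discontinuation cell is the more important of the two. It affects every participant, including the TDF plus PI/r group that objective 1.3.2 is about, and drug-related toxicity is the first reason listed for stopping in Protocol 8.1. The column also serves participants who leave the study altogether, for whom no R+4 visit follows.

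At stake is the reading of the renal listing. A participant with no listed urine event may have been tested at the end of treatment, or may not have been tested for weeks, and the report would not show which.

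**Working it through.** No sample size or error rate is involved. The check is a column reading of the schedule plus simple date arithmetic.

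**1. Is the column reading sound?** The uric acid row of the same table, read the same way, gives entry, week 12 and week 24. Protocol 6.3.7 confirms this: "Uric Acid: required at weeks 0, 12, and 24". The CrCl, INR and stored urine rows each show a mark in the premature discontinuation column; the urinalysis row does not. The blank is therefore not a fault of alignment.

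**2. Scheduled post-entry urinalyses for completers.**

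| Group | Visits | Count | Test at end of treatment? |
|---|---|---|---|
| Arm A, TDF plus PI/r | 1, 2, 4, 8, 12, R+4 | 6 | Yes (week 12) |
| Arm A, others | 4, 12 | 2 | Yes (week 12) |
| Arm B, TDF plus PI/r | 1, 2, 4, 8, 12, 16, 20, 24, R+4 | 9 | Yes (week 24) |
| Arm B, others | 4, 12, 20 | 3 | No |

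**3. Length of the late Arm B gap.** SAP 2.6 gives windows of days 133–147 for week 20 and 161–175 for week 24.
- Nominal: 168 − 140 = 28 days, and 28/168 = 16.7% of the course.
- Shortest by the windows: 161 − 147 = 14 days.
- Longest by the windows: 175 − 133 = 42 days.

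**4. Early stoppers.**
- On TDF plus PI/r: urinalysis is scheduled at every on-treatment visit, so the last one is nominally at most 4 weeks old. The next is at R+4 (R+23 to R+35 days), if the participant stays on study.
- Others: universal tests are at entry and weeks 4, 12 and 20, so the last one can be up to 8 weeks old. A stop at week 11 leaves 11 − 4 = 7 weeks. A stop before week 4 leaves only the entry test. No urinalysis is scheduled afterwards.
- If a stop falls at a visit that already has a mark, that test serves.

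**5. Do other provisions fill the gap?**
- *Creatinine or CrCl trigger (7.1.3.1).* CrCl below 50 mL/min, or a creatinine rise of at least 0.4 mg/dL from entry, requires a urinalysis within 7 days. CrCl is scheduled at week 24 and at premature discontinuation, so an event with a filtration change is followed up.
- *Spot protein and creatinine (6.3.7).* After a trigger, this continues through R+4 until resolution. It does not start without one.
- *Stored urine (6.3.10).* "Urine will be collected and stored for evaluation of retinol binding protein, beta-2 microglobulin, and creatinine". These analytes do not supply dipstick protein or glucose.

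What remains uncovered is a new or increased dipstick finding with no creatinine or CrCl trigger.

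**6. How often would the discontinuation cell matter?** The protocol gives no rate for this population. As an assumption, the 98.1% completion in the phase III ION studies (2.3.3) would imply 1.9% × 40 = 0.76 early stoppers in the planned trial and 1.9% × 7 = 0.13 in the enrolled one. This harder-to-treat, coinfected population may differ.

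**The case against.** The best defence is that lighter testing outside TDF plus PI/r is deliberate. Protocol 6.3.7 says that urinalysis frequency depends on ARV regimen, 2.2 identifies PI/r users as the group of most concern for raised tenofovir, and objective 1.3.2, as amended, concerns TDF plus PI/r. That group is tested at every on-treatment visit and at R+4. This stands as a reason for fewer visits. It does not explain the blank discontinuation cell, which affects the target group too, or why end of treatment is covered for everyone in Arm A but not in Arm B. Nor are the others free of the interaction: TDF with non-PI/r regimens is allowed (4.1.5), and the Letter of Amendment says that LDV/SOF raises tenofovir when given with TDF.

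A second defence is that the safety net works, because creatinine and CrCl triggers lead to a urinalysis and the site may add toxicity follow-up after an early stop (6.2.5). This also stands. A reader might infer that late or pre-stop urine events cannot be detected; the documents do not support that. They have no scheduled test unless something else triggers one.

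A third is that the matter is now largely moot. Accrual closed on July 21, 2016, and 168 days later is January 5, 2017, the day before the call cited in SAP 2.9. Dosing was therefore essentially over when SAP 2.0 was written. This limits what an amendment can do for these participants, but it does not affect how the listing should be read.

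**Conclusion.** The gap is real but minor. Two cells of one row do not match the outcome they serve: premature discontinuation for all participants, and week 24 for Arm B outside TDF plus PI/r. The uncovered time is nominally 28 days late in Arm B (14 to 42 by the windows) and up to 8 weeks before an early stop outside TDF plus PI/r. The loss is confined to isolated dipstick changes. The outcome is secondary, the analysis is descriptive, and 7 participants were enrolled.

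Three stronger readings are not supported:
- *That the urine limb goes unmeasured whenever treatment ends.* Arm A completers and Arm B completers on TDF plus PI/r are tested at end of treatment.
- *That the schedule biases Arm B downward against Arm A.* Outside TDF plus PI/r, Arm B has three post-entry tests and Arm A has two, so for an ever-occurred outcome the direction is not established. Between-arm intervals are planned only for SVR (9.6), and renal events are only described and listed.
- *That 25 of 40 participants, and hence about 12 or 13 in Arm B, were planned to fall outside TDF plus PI/r.* The 25 is an enrolment cap for the first 3 months, and 9.3 sets no minimum or maximum for the TDF plus PI/r group.

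The conclusion assumes that the schedule is followed as printed and that sites add no unscheduled urinalyses.

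**What to change.** In the urinalysis row of the Schedule of Events:
1. Add a mark in the premature treatment/study discontinuation column for all participants.
2. Remove superscript 3 at week 24 and keep the unrestricted mark at week 20.

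Both arms then have an end-of-treatment urinalysis for everyone. Exchanging the week 20 and week 24 entries would use the same number of tests, but it would leave Arm B participants outside TDF plus PI/r untested from week 12 to week 24. That is 12 weeks, against a longest scheduled on-treatment interval of 8 weeks now, so it should not be done.

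The cost is one dipstick per affected participant (with the reflex microscopy already specified if it is abnormal), at visits where urine is already collected for storage, plus a letter of amendment.

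For participants already past those visits, the remedy is in reporting. The SAP 4.2.1(c) listing shows urine results only for participants who had an event. It should be extended to give, for every treated participant, the time of the last urinalysis relative to the last dose, so that the absence of an event is not read as the absence of toxicity. With 7 participants this is at most seven lines.
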